Considering that the ONLS is the best assessment method of disability, a clinically relevant endpoint in CMT1A, and it has been recently shown to be more sensitive to change than the CMTNS, the ONLS is selected as primary endpoint.

B. CMTNS is a specific scale designed to assess severity of impairment in CMT disease (Shy, 2005). Although not completely validated, it provides a single and reliable measure of CMT severity. It is a 36-point scale based on 9 items: 5 of them quantify impairment (sensory symptoms, pin sensibility, vibration, arm and leg strength), 2 activity limitations (motor symptoms arms and legs) and 2 electrophysiological data (amplitudes of ulnar Compound Muscle Action Potential [CMAP] and Sensory Nerve Action Potential [SNAP]). Increased scores indicate a worsening of the function: the scores categorize a disability as mild (0-10), moderate (11-20) and severe (21-36).

While CMTNS score is commonly used to assess disease severity, it may be problematic to evaluate the potential clinical benefit of a drug; as it is a composite score based on patient signs, symptoms, and on electrophysiological data with potentially very different meanings and interpretations, an objective analysis may be difficult.

Nevertheless, CMTNS is an accepted measure of CMT severity, but its sensitivity to change is debated (Reilly, Shy *et al.*, 2010). Some CMTNS components are apparently not sensitive enough, and floor/ceiling effects do occur. For instance, if the patient had surgery (fixation of the ankle), the 'motor leg symptoms' definitively score 3; so, it is not possible to get a decrease of the score whatever it happens. The usefulness of the SNAP component was also judged to be limited as it is frequently absent in CMT1A patients which receive the maximum score on their entry visit, thus has a low sensitivity to change. (Komyathy, Neal *et al.*, 2013) pointed out that sensory and motor symptoms items result from subjective opinion from patients, concerning their leg and arm strengths and loss of sensation in their legs, and that pin sensibility, vibration and strength are based on a neurological examination which depends on patient cooperation and examiner consistency to obtain reproducible results. Finally, some measurement of the CMTNS, such as SNAP or vibratory sensation, may decrease normally with age; thus, scores could increase slightly as age for reasons independent of CMT (Shy, 2005).

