CMAP measures conduction of nerve impulses better than the conduction velocities that are affected in CMT1A since a very early age. An improvement of the patient requires an increase of the CMAP. However, electrophysiological parameters are measured on more or less severely impaired and atrophic distal muscles, but it is well recognized that an improvement usually first appears in the less affected proximal parts. Consequently and in our context, the sensitivity of the CMAP remains limited. The same applies for NCV, but it is the CMAP that prevails.

Sensory measures (SNAP and SCV) are less reliable than motor ones due to their very high sensitivity to electrodes positioning. SNAP is affected by the cutaneous impedance that varies with the sub-dermal tissue thickness (~obesity). Moreover, in CMT1A, amplitudes are close to zero, so that conduction velocity is not measurable. These values are of a limited use. Finally, as missing value of SNAP might be a characteristic of severity, disregarding missing values for severe patients, and using for other patients may introduce a bias. Under a given threshold, amplitudes disappear as they stand below the lower level of detection or are measured on highly altered fibers; this anomaly can also be related to other non-specific factors, such as lesions of the skin). This 'grey zone' does not correspond to a zero but certainly to a very low value difficult to measure.

A quick axonal regeneration after a 1-year treatment is not realistic. However, an indirect recurrence of potentials is still plausible after resynchronisation of remyelinated fibers and summation of the potentials of each fiber. Indeed, the demyelination of fibers induces a desynchronisation leading to the dispersion of the electric signal which reduces its amplitude to zero. A positive effect after a 1-year treatment is more likely to be observed on the conduction velocities rather than on amplitudes.

The electrophysiological parameters considered here measure more a putative distal effect of the treatment rather than a proximal one that is however more likely to be observable at first. To the end to measure a proximal effect, electrophysiological measures on the sciatic nerve would represent an ideal alternative, but technical constraints are not well controlled.

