14.4 Secondary efficacy analyses

The primary ANCOVA analysis based on the summary mean at 12 and 15 months will be repeated on the other quantitative efficacy endpoints (see above). The significance of the treatment effect on each quantitative endpoint will also be evaluated based on the difference compared to Placebo in change from baseline at each individual visit and in slope of progression over the duration of the study. The proportion of responders at 15 months will be assessed through a Generalized Linear Mixed Model (GLMM) featuring logistic regression, and admitting center as a random effect. Secondary analyses will be conducted at a two-sided 5% significance level.

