14.5 Missing data

Few missing data were observed in past trials in this pathology. Due to likely expected loss of efficacy after treatment discontinuation, and a possible deterioration compared with baseline values, last or baseline observation carried forward may not be appropriate. Missing values will be imputed using a linear model estimated on the Placebo group. The potential impact of missing data on the study's conclusions will be evaluated. Descriptive data analyses will allow assessing the pattern of missing data, including reasons for drop-outs in each treatment group. In addition, sensitivity analyses will be conducted by using other missing data approaches (further details in the SAP).

For any patient experiencing early trial interruption, an early interruption visit is planned. It will be checked if this visit took place within a given time frame where the next regular visit would have been planned. In case the early interruption visit occurs within this time frame, data of the early interruption visit will be shifted to the next regular visit for all analyses. In case the early interruption visit does not occur within this time frame, the data of the early interruption visit will not be included in any of the inferential analyses.

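### Section 14.5 makes no exception for SNAP amplitudes below detection, so its placebo-model imputation, read literally, would replace very low values with typical detectable ones

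*Combined protocol and SAP*

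**What the plan says.** Section 8.4.1.3 discusses SNAP twice. Under CMTNS it notes that "it is frequently absent in CMT1A patients". Under electrophysiological parameters it refers to a missing SNAP value as a possible sign of severity and warns that "disregarding missing values for severe patients, and using for other patients may introduce a bias". Of amplitudes below the detection threshold it says: "This 'grey zone' does not correspond to a zero but certainly to a very low value difficult to measure". It adds that "this anomaly can also be related to other non-specific factors, such as lesions of the skin". On sensory velocity it says only that "amplitudes are close to zero, so that conduction velocity is not measurable".

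Section 14.4 says that the primary ANCOVA, on the mean of months 12 and 15, "will be repeated on the other quantitative efficacy endpoints", and sets a two-sided 5% level for secondary analyses. Section 14.5 gives the handling rule: "Missing values will be imputed using a linear model estimated on the Placebo group". It promises sensitivity analyses by other approaches and leaves their detail to the SAP.

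Section 8.4.1.2 places SNAP under exploratory efficacy endpoints; the synopsis lists it as secondary. In Appendix 3, CMTNS-v2 scores a radial sensory amplitude below 1 µV as 4, the worst category.

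**The concern.** The protocol identifies the hazard in one section and does not address it in the section that governs the analysis. An absent SNAP usually carries information: the amplitude is too low to record. A linear model fitted to placebo patients can learn only from amplitudes that were recorded, so its predictions lie in the detectable range. Such a prediction for a non-recordable response turns one of the lowest values in the trial into an ordinary one.

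The error does not cancel between arms when treatment works. A treated patient whose response reappears just above the limit enters with a true low value. A comparable placebo patient whose response stays absent enters with a higher, imputed value. The improvement then counts against treatment. At stake is the interpretation of SNAP amplitude as pharmacodynamic evidence; the primary claim is not involved.

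**Working it through.** **1. The plan's own figure.** There is no sample size for SNAP. The only one is for ONLS (14.3: R = 0.75, SD about 1, difference 0.3, two-sided 2.5%, power 90%). With two post-baseline measures under compound symmetry, the variance is (1 + 0.75)/2 − 0.75² = 0.3125. Then n = 2 × (2.241 + 1.282)² × 0.3125 / 0.3² = 86.2, so 87 per group (88 with the t distribution) against 89 stated. This reproduces, and nothing below alters it.

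**2. Assumptions needed.** The documents give no absent fraction, SD, correlation or effect for SNAP, so all are assumed and varied. Section 14.5 names no covariates for its linear model. The simulations regress follow-up on baseline in placebo patients with both values recorded, and set an absent baseline to the observed placebo mean. They use one follow-up value instead of the mean of two.

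**3. Bias, normal scale.** Latent amplitude has SD 1, and follow-up = 0.75 × baseline + √(1 − 0.75²) × noise + effect. The detection limit is placed so that 20%, 40% or 60% are absent at baseline. There are 20,000 patients per arm, averaged over 10 runs. The true effect is +0.30 in all treated patients.

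| Absent | Full data | Placebo-model imputation | Absent set at limit |
|---|---|---|---|
| 20% | 0.304 | 0.180 | 0.255 |
| 40% | 0.301 | 0.104 | 0.198 |
| 60% | 0.300 | 0.052 | 0.137 |

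The loss under imputation is 1 − 0.180/0.304 = 41%, 1 − 0.104/0.301 = 65% and 1 − 0.052/0.300 = 83%. Setting absent values at the limit also attenuates, but less. With no true effect, imputation gives −0.001 to 0.001.

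**4. Response only in patients absent at baseline.** Section 8.4.1.3 considers a return of potentials plausible. With +0.30 in those patients only, the full-data effects of 0.060, 0.118 and 0.181 become −0.011, −0.012 and −0.010 under imputation. Setting absent values at the limit keeps the sign (0.029, 0.041, 0.046).

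**5. Power, log-normal scale.** Log SD 1, limit 1 µV (the CMTNS-v2 cut-off), 90 per arm, +0.3 in log amplitude, two-sided 5%. With 50% absent the median is 1 µV, and the true difference is exp(0.5) × (exp(0.3) − 1) = 1.649 × 0.350 = 0.58 µV. Responses truly below 1 µV are imputed at about 2.5 µV on average, and at correlation 0.9 the estimated difference is 0.32 to 0.35 µV.

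| Absent | Correlation | Placebo-model imputation | Rank ANCOVA, absent lowest |
|---|---|---|---|
| 30% | 0.9 | 57–58% | 98% |
| 50% | 0.9 | 39% | 91% |
| 50% | 0.75 | 27% | 67% |
| 70% | 0.9 | 20–25% | 73–74% |

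The imputation figures move by several points with small implementation choices (37% to 42% in the second row), so only the ordering and rough size should be read. Both methods keep a null error rate near 5%, so the rank gain is not inflation.

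**6. How much is the coding.** In the run giving 37% and 92% at 50% absent, substituting half the detection limit gave 83%. Of the 92 − 37 = 55 points, 83 − 37 = 46 come from how absent values are coded; the other 9 reflect the choice of ranks over µV.

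**7. Sign reversal in µV.** With 50% absent, correlation 0.9 and +0.6 log only in patients absent at baseline, the true mean difference is exp(0.5) × Φ(−0.9) × (exp(0.6) − 1) = 1.649 × 0.184 × 0.822 = 0.25 µV. Imputation gives about −0.13 µV.

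**The case against.** The best reply is that no section says how a tested but absent response is recorded: as missing, as zero or as below 1 µV. The reasoning in 14.5 is about drop-out and early interruption, and CMTNS-v2 scores the absent response, so it is not missing there. That stands as far as it goes: a reader might infer that absent SNAP will certainly be imputed, and the documents do not establish this. But 8.4.1.3 itself uses the word missing for an absent SNAP, the imputation rule in 14.5 is unqualified, and what 14.5 leaves to the SAP is the sensitivity analyses.

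Other limits also stand:

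- A reader might extend the very-low reading to conduction velocity. The protocol says it of amplitudes only; velocity without a potential is not measurable, hence undefined.
- Severity is offered as a possibility, and skin lesions and other non-specific causes are named. Ranking every absent response lowest would misclassify those.
- Section 8.4.1.3 regards sensory measures as less reliable than motor ones and of restricted value, and expects early benefit on velocities more than on amplitudes. It does not make SNAP the main pharmacodynamic evidence.
- The assumed effect is large. In baseline-adjusted SD units it is 0.3/√(1 − 0.9²) = 0.69 at correlation 0.9 and 0.3/√(1 − 0.75²) = 0.45 at 0.75.

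**Conclusion.** The concern holds as a conditional one. If non-recordable SNAP amplitudes count as missing, as the wording of 8.4.1.3 suggests, the rule in 14.5 conflicts with the protocol's own reading of what they mean. A uniform true effect is then attenuated, by about 41% to 83% for 20% to 60% absent under the normal-scale assumptions, and an effect confined to patients absent at baseline is erased or changes sign. The power figures are illustrations on assumed inputs.

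It would be wrong to infer that every treatment effect simply shrinks, since the result depends on who responds, or that false positives arise, since a true null stays null. Nor can one say in general that most of the power is lost: with 30% absent and correlation 0.9, 57% to 58% remains against 98%. The scope is the secondary or exploratory SNAP amplitude analysis. ONLS, its sample size and the SNAP item in CMTNS-v2 are unaffected. The change is worth making because it is cheap and the protocol has already named the bias.

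**What to change.** In 14.5, define two categories for each SNAP assessment: test done with response not recordable, and test not done or technically invalid (for example because of a skin lesion). Assign them before unblinding.

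- **Not recordable:** analyse SNAP amplitude by rank ANCOVA with these responses at the lowest rank, or by a model left-censored at the detection limit. Treat baseline and follow-up alike. Report the proportion recordable and medians by arm.
- **Not done or invalid:** keep the placebo-model imputation.
- **Conduction velocity:** prespecify a separate rule for when no potential is recorded, and do not assume that the velocity is low.

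The cost is SAP wording, one alternative model and a check that the recorded data distinguish the two categories. The downside is that a rank result is less directly expressed in µV, which the medians and proportion recordable partly offset. A left-censored model stays on the amplitude scale but relies on a distributional assumption.

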8.4.3 Other exploratory endpoints

8.4.3.1 PXT3003 components plasma concentration

Plasma concentrations of baclofen, naltrexone and 6 β -naltrexol, PXT3003 components will be dosed on blood samples performed (on lithium heparinised tubes) at inclusion visit and at 6-month (V3), 12-month (V5) and 15-month (V6) visits to determine PK parameters of the 2 tested doses.

Blood samples will be performed at through (i.e. pre-dose in the morning) and at peak (i.e. 90 minutes after drug administration), and they will be stored at -80°C and analyzed in the central laboratory (Bertin Pharma, Orleans, France).

8.4.3.2 Blood biomarkers, gene expression analyses and DNA sequencing

Plasma samples for biomarkers identification will be performed at inclusion visit and at 6-month (V3), 12-month (V5) and 15-month (V6) visits, and they will be stored at -80°C.

This exploratory work on biomarkers should be considered only for research purposes and not as data that have to be delivered to patients or to health authorities at the end of this Phase III.

Pharnext has identified potential blood biomarkers (Tryptophan, Alanine, Serotonin, Thyroxin (T4), and free cholesterol) in the previous phase II that need to be confirmed in this phase III.

Meanwhile, other markers could be assessed for quantification studies, and thus identified later after the accomplishment of this clinical trial. On the other hand, from the same drawn samples, leucocytes will be isolated for gene expression studies (microarrays and PCRs).

Leucocytes will be isolated from an additional sample drawn at the inclusion visit only in order to realize DNA sequencing for all included patients after they have given their written informed consent for research purposes. One of the purposes of genome sequencing could be to advance the understanding CMT1A disease for the research community in general. It should be possible to identify genes that could change in response to PXT3003 treatment, which could confer them the property of pharmacodynamics candidates. Furthermore, gene expression analysis could be very valuable for the study of mechanisms occurring in CMT1A, which has never been performed before with such blood samples. For Instance, novel mutations in CMT1A patients, excluding those of CMT, could be discovered and associated with various mechanisms underlying the mildness or severity of the disease. On the other hand, correlations of sequencing data with clinical scores and endpoints are also relevant for the study of the pharmacodynamics of PXT3003 for a future potential development of personalized medicine. To this end, it is of interest to get benefit from such clinical studies as the one described here in this protocol to perform DNA sequencing because CMT1A patients are rare, which could substantially contribute to the improvement of the field. For these reasons, this sequencing study should be considered only for

research purposes and not as data that have to be delivered to patients or to health authorities at the end of this Phase III.

8.4.3.3 Biomolecular changes in skin biopsy (Optional ancillary sub-study)

Volunteer centers that agree to perform skin biopsies (according to their interest, available equipment and resources) will participate to this ancillary sub-study to assess candidate genes (biomarkers) by microarrays and RT-qPCR technics. Candidate genes will be selected based on ongoing assessments and analyses of skin biopsies derived from Phase II CMT1A patients and from other CMT1A cohorts generated by Pharnext. This exploratory study aims to identify genes that could change in response to PXT3003 treatment, which could confer them the property of pharmacodynamics candidates. Furthermore, gene expression analysis could be very valuable for the study of mechanisms occurring in CMT1A, which has never been performed before with such skin biopsy samples. Skin biopsies are of great value because of their rarity. This is why we would like to take the benefit of the Phase III trial to access these samples for research purposes.

One small punch biopsy will be performed at the ankle level of one leg at the inclusion visit (V1) and at the end of the treatment at the 15-month visit (V6). Separate protocol will define the methodology.

8.4.3.4 MRI of leg to assess muscle/fat index (Optional ancillary sub-study)

MRI is a method to identify areas of muscle atrophy and fatty infiltration in the legs that are hallmarks of disease severity and are due to the progressive degeneration of axons without concomitant re-innervation, resulting in progressive denervation of muscle. Del Porto *et al.* (2010) showed in CMT that changes in MRI signal intensity, reflecting muscle atrophy and fatty infiltration, are associated with changes in dorsiflexion strength and areas of acute denervation processes or injury. MRI shows areas where muscle has been replaced by fat, a process which occurs in neuropathies.

MRI of the leg will be performed at baseline and at the end of the study (Visit 6). In particular for example the anterior muscle compartment responsible for foot dorsiflexion (tibialis anterior, extensor hallucis longus, extensor digitorum longus and peroneus tertius) (del Porto, Nicholson *et al.*, 2010)..

Short Tau Inversion Recovery images will be acquired in the axial plane to delineate these structures and to assess changes in signal intensity as an indicator for acute denervation and/or possible injury (Gallardo, Garcia *et al.*, 2006).

The MRI examination will look for signal intensity alterations including muscle edema, fatty infiltration, and abnormal contrast enhancement. Increase of T1 signal intensity in the muscle belly due to fatty infiltration will be estimated in a semi-quantitative way, according to the Goutallier's classification (Schiefer, Mendonca *et al.*, 2015).

A specific technical manual will be written separately to ensure the standardization of MRI acquisition across all sites, and centralized reading will be organized.

9. SELECTION OF PATIENTS

The study will be performed in **genetically proven CMT1A patients, aged from 16 to 65 years, with mild to moderate severity and muscle weakness in at least foot dorsiflexion.**

It is planned to randomize at least **300 patients** [100 /arm] with the following selection criteria:

9.1 Inclusion criteria

- 1- Male or female, aged from 16 to 65 years;
- 2- Patient with a proven genetic diagnosis of CMT1A;
- 3- Mild to moderate severity assessed by the Charcot-Marie-Tooth Neuropathy Score (modified version 2) CMTNS-V2, with a score >2 and ≤18;
- 4- Muscle weakness in at least foot dorsiflexion (clinical assessment);
- 5- Motor nerve conduction of the ulnar nerve of at least 15m/sec;
- 6- A written informed consent to participate in the study is signed by the patient and he is willing and able to comply with all the study procedures and the scheduled visits.

9.2 Exclusion criteria

Patients who have met all the above inclusion criteria listed will be screened for the following exclusion criteria:

- 1- Any other associated cause of peripheral neuropathy such as diabetes;
- 2- Patients with another significant neurological disease or a concomitant major systemic disease;
- 3- Clinically significant history of an unstable medical illness since the last 30 days (unstable angina, cancer...) that may jeopardize the participation in the study;
- 4- Significant hematologic disease, hepatitis or liver failure, renal failure;
- 5- Limb surgery within six months before randomization or planned before completion of the trial;
- 6- Clinically significant abnormalities at the pre-study clinical examination, routine laboratory evaluations and electrocardiogram (ECG);
- 7- Elevated AST/ALT (>3 x ULN) and/or elevated serum creatinine levels (>1.25 x ULN);
- 8- History of recent alcohol or drug abuse or non-adherence with any treatment or other experimental protocols;
- 9- Patients using unauthorized concomitant treatments including but not limited to baclofen, naltrexone, sorbitol (pharmaceutical form), opioids, levothyroxin and potentially neurotoxic drugs such as amiodarone, chloroquine, cancer drugs susceptible to induce a peripheral neuropathy; (list provided in appendix 1). Patients who can/agree to stop these medications 4 weeks before randomization and during the whole study duration can be included;
- 10- Women of child bearing potential not using highly-effective method(s) of birth control (ie, with low failure rate <1% per year) throughout the study and/or unwilling to be tested for pregnancy; Pregnancy or breast feeding;
- 11- History of safety issues or known hypersensitivity to baclofen, naltrexone or sorbitol, or to any of the individual components of PXT3003;
- 12- Any contraindication to use of baclofen (e.g. porphyria), naltrexone or sorbitol as defined in the national product labels;
- 13- Suspected inability to complete the study follow-up (transient visitors, tourists or any patient for whom the follow-up evaluation would be too difficult to appreciate for any reason);

- 14- Limited mental capacity or psychiatric disease rendering the subject unable to provide written informed consent or comply evaluation procedures;
- 15- Patients who have participated in another trial of investigational drug(s) within the past 30 days;
- 16- If a patient from the same family, living in the same household, has already been included in this study, it will not be possible to include another patient from the same family to avoid mixing of therapeutic units; therefore there would be a risk of inversion of the blind treatments which could jeopardize the interpretation of study results.

